7.3.1. Background

The following infolmation should be recorded in the registration foml for patient registration (see 7.6.4).

- 1. ID number
- 2. Gender
- 3. Month of birth or age (at the time when the treatment of XELJANZ is planned to be commenced)
- 4. Planned first day of treatment with XELJANZ•
 - *: Date when treatment with the couunercial product of XELJANZ is started for patients who participated in clinical trials
- 5. Confirmation of eligibility for XELJANZ treatment (confirm that patients do not meet the contraindications in the latest package insert)
- 6. Confirmation of eligibility for the investigation

7.3.2. Pre-dosing observation

The following information should be recorded in CRF.

- 1. Height
- 2. . Body weight
- 3. Information on ulcerative colitis
 - a. Name of the disease
 - b. Date of diagnosis or duration of the disease
 - c. Extent of the lesion · (total colitis, left-sided colitis, proctitis, right-sided or segmental colitis)
 - d. Severity* (sever, moderate, mild; See Table 3.)

	rable 5. Classification of dicerative contributy sevenity				
	Severe	Moderate	Mild		
l) Frequency of stool	6 times or more	Intermed iate	4 times or less		

Table 3. Classification of ulcerative colitis by severity.

Xeljanz A3921248NON-INTERVENTIONAL STUDY PROTOCOL Version 5 (Amended 4). 17 December 2019

2) Obvious	(+++)	between severe	(+) to (-)	
bloody stool		and mild		
3) Fever	37.5°C or higher		(-)	
4) Tachycardia	90/min or more		(-)	
5) Anemia	Hb 10 g/dL or less		(-)	
6) Erythrocyte				
sedimentation	30 mm/h or more		Normal	
rate				
Note:				
• Rated as sev	ere when criteria 1), 2	2), and one of the syste	emic symptoms 3)	
alld 4) are s	atisfied, and at least 4	of the 6 criteria are sa	atisfied.	
• Rated as mil	d when all of the 6 cl	literia are satisfied.		
• Among patients with severe disease, those showing extremely severe symptoms are classified as having fululinant disease, and, depending on the				
rapidity of the disease onset. fuhninant disease is subdivided into acute				
fuhninant and relapsing fuhninant disease.				
• Patients satisfying all of the following 5 criteria are classified as having fulminant d isease.				

- 1. Satisfying the criteria for severe disease
- 2. Bloody diarrhea occurring at a frequency of 15 times/day or more
- 3. Persistent high fever (38°C or higher)
- 4. Increase of the leukocyte count to $10,000 \,/\text{mm}^3$ or more
- 5. Severe abdominal pa in

*: Criteria for diagnosis and treatment strategy for ulcerative colitis and Crohn's disease 2016 revised version (supplementary volume of the 2016 annual report of "Research Group of Intractable Inflammatory Bowel Disease" [Suzuki Group], Research on Policy Planning and Evaluation for Rare and Intractable Diseases, Health and Labom Sciences Research Grants)

- **: Patients with nlild disease ale not eligible for XELJANZ treatment.
- e. Status of refractory ulcera tive colitis based on treatment response (status of steroid dependency or resistance in the last episode before commencement of XELJANZ treatment)
- 4. Status of pregnancy (female patients only)
- 5. Medical history (name of disease or syndrome (diagnosis], classification of history or concurrent disease..)
 - * History: Chronic disease (including allergy), disease requiring treatment, disease or disorder with surgery, hospitalization or sequelae, and other relevant disease or syndrome that are cured before commencement of XELJANZ treatment (no treatment and no symptoms)
 - * Concurrent disease: Chronic disease (including allergy), disease requiring treatment disease or disorder with surgery, hospitalization or sequelae, and other relevant disease or syndrome that require any treatment or require no treatment but have residual symptoms at the time of commencement of XELJANZ treatment

6. Prior treatment for ulcerative colitis

The status of prior treatment (drug and non-drug therapy) for the last episode before commencement of XELJANZ treatment (an episode treated with XELJANZ) should be recorded.

For biological products, the status of use throughout the past treatment of ulcerative colitis should be recorded, and if any biological product was used, the name of the product and the classification of primary failure or secondary failure• should be recorded.

*: Primary failure: Lack of effectiveness or insufficient effectiveness with treatment for an appropriate period at the approved dosage and administration

Secondary failure: Loss of effectiveness (relapse) with continued treatment after achieving a clinical response (remission) with treatment for an appropriate period at the approved dosage and administration

Indeterminate: Treatment is discontinued due to any reason other than "not effective" (e.g., adverse events) and determination whether it is primary failure or secondary failure cannot be made

- 7. Smoking history (status of smoking at the start of the investigation)
- 8. Family history of malignant tumor (including lymphoma)

7.3.3. XELJANZ use record

The record of the status of XELJANZ treatment from the date of treatment commencement to the date of completion of the observation period (or date of XELJANZ discontinuation) should include the following information.

However, for patients who are treated with XELJANZ for more than 60 weeks after the date of treatment commencement, information until the end of the investigation period (or date of XELJANZ discontinuation) should also be recorded.

- 1. Dose
- 2. Number of doses per day
- Reason for change or intenuption•
 *: Reason for a change in the dose or the number of doses per day if any
- 4. Duration of treatment
- 5. Reason for continued treatment at Week 16 of treatment*
 - *: Reason for continuation of XELJANZ treatment beyond Week 16 despite no therapeutic response in induction therapy at Week 16 based on clinical symptoms, endoscopy and other findings

7.3.4. Concomitant therapy for ulcerative colitis

7.3.4.1. Drug therapy

The record of treatments• for ulcerative colitis used from the date of commencement of XELJANZ treatment to the date of completion of the observation period (or date of XELJANZ discontinuation) should include the following information.

- 1. Drug name
- 2. Route of administration
- 3. Dosage form (topical agents only)
- 4. Duration of treatment
 - *: 5-ASAs (oral, enema, suppository), steroids (oral, enema, suppository, injection), immunomodulators (oral, injection), biological products (injection)

7.3.4.2.Non-drug therapy

The record of non-drug treatments given from the date of commencement of XELJANZ treatment to the date of completion of the observation period (or date of XELJANZ discontinuation) should include the following information.

- 1. Name of the therapy
- 2. Period of administration
- 3. Reason for the administration of non-drug therapy

7.3.5. Status of vaccination

The record of vaccines given in relation to the treatment of ulcerative colitis should include the following information from baseline to the date of completion of the observation period (or date of XELJANZ discontinuation).

- 1. Herpes zoster vaccine: Status and date of vaccination, drug name (vaccine name)
- 2. Pneumococcal vaccine: Status and date of vaccination

7.3.6. Status of prophylactic treatment

The record of the status of prophylactic treatment given from 3 months before the commencement of XELJANZ treatment to the date of completion of the observation period (or date of XELJANZ discontinuation) should include the following information.

- 1. Classification: Tuberculosis, Pneumocystis jirovecii pneumonia, hepatitis B
- 2. Drug name (product name)
- 3. Duration of treatment

7.3.7. Tests/clinical laboratory tests

The record of the following tests conducted from baseline to the date of completion of the observation period (or date of XELJANZ discontinuation) should include the status, dates and results (or findings) of the tests. **If** the abnormal change is clinically

significant compared to the baseline value, this information should also be recorded in the adverse event field.

7.3.7.1. Clinical laboratory tests

Results of the following clinical laboratory tests conducted from baseline (within 1 month before treatment commencement, including the date of treatment commencement*) to the date of completion of the observation period (or date of XELJANZ discontinuation).

1. Hematology White blood cell count, neutrophil, eosinophil, lymphocyte, monocyte, red blood cell count, platelet count, hemoglobin

- 2. Blood chemistry AST (GOT), ALT (GPT), AL-P, LDH, total cholesterol, HDL-C, LDL-C, y-GTP, total bilirubin, triglyceride, serum creatinine, creatine kinase, albumin
- 3. Other tests KL-6, -D-glucan, BUN, fecal calprotectin, CRP

*: Within 3 months before treatment commencement for fecal calprotectin

7.3.7.2.Chest X-ray test or chest CT test

Findings of chest X-ray or chest CT conducted from baseline (within 3 months before treatment commencement, including the date of treatment commencement) to the date of completion of the observation period (or date of XELJANZ discontinuation).

7.3.7.3.Tuberculosis screening tests

Results of the following tests conducted from baseline (within 6 months before treatment commencement, including the date of treatment commencement) to the date of completion of the observation period (or date of XELJANZ discontinuation).

- 1. Interferon *y* release assay (QuantiFERON, T-SPOT)
- 2. Tuberculin skin test
- 7.3.7.4.Blood pressure (systolic/diastolic)

Results of measurements from baseline to the date of completion of the observation period (or date of XELJANZ discontinuation).

7.3.7.5.Hepatitis B and C virus tests

Results of the following tests conducted within 3 months before treatment commencement should be recorded. For patients who are HBV carriers, the status of HBV-DNA test conducted up to the completion of the observation period (or date of XELJANZ discontinuation) should be recorded.

- 1. Hepatitis B virus test: HBs antigen, HBs antibody, HBc antibody, and HBV-DNA test
- 2. Hepatitis C virus test: HCV antibody

7.3.7.6.Colonoscopy

Results of colonoscopy (inflammation site and findings) conducted from 6 months before commencement of XELJANZ treatment to the date of completion of the observation period (or date of XELJANZ discontinuation).

7.3.8. Clinical evaluation on effectiveness

The record of the clinical evaluation on effectiveness against ulcerative colitis from baseline (including the date of treatment commencement) to the date of completion of the observation period (or date of XELJANZ discontinuation) should include the results of evaluations based on the following rating scales.

1. Stool frequency:

0 point = Normal number of stools for the patient

1 point = 1-2 stools more than normal

2 points = 3-4 stools more than normal

- 3 points = 5 or more stools more than normal
- 2. Rectal bleeding:
 - 0 point = No blood seen
 - 1 point = Slight of blood with stool less than half the time
 - 2 points =Obvious blood with stool most of the time
 - 3 points = Blood alone passed
- 3. Findings of flexible sigmoidoscopy:
 - 0 point = Normal or inactive disease
 - 1 point = Mild disease (erythema, decreased vascular pattern, mild fragility)
 - 2 points = Moderate disease (marked erythema, absent vascular pattern, any friability, erosion)
 - 3 points = Severe disease (spontaneous bleeding, ulceration)
- 4. Physician's global assessment:
 - 0 point = Normal
 - 1 point = Mild disease
 - 2 points = Moderate disease
 - 3 points = Severe disease

7.3.9. Status of pregnancy (female patients only)

The status of pregnancy from the date of commencement of XELJANZ treatment to the date of completion of the observation period (or date of XELJANZ discontinuation) should be recorded. However, for patients who are treated with XELJANZ for more than 60 weeks after the date of treatment commencement, the status of pregnancy until the end of the investigation period (or date of XELJANZ discontinuation) should also be recorded.

7.3.10.Status of treatment with XELJANZ

The status of treatment with XELJANZ at the completion of the observation period for each booklet (Week 26, Week 60, end of the investigation) should be confirmed, and the following information should be recorded. If the reason for discontinuation at the last observation is an adverse event or patient's death, its details should be recorded in the adverse event field.

- 1. Date of the last observation
- 2. Completion of treatment or reason for discontinuation
 - Completed (treatment continued)
 - Adverse events (Record the details in the adverse event field)
 - Patient's death (Record the date of death)
 - Remission
 - Insufficient clinical effectiveness
 - Failure to show up
 - Other

7.3.11.Adverse events

The status of occurrence of adverse events from the date of commencement of XELJANZ treatment to the date of completion of the observation period (or date of XELJANZ discontinuation) should be confirmed, and the following information should be recorded. However, for patients who are treated with XELJANZ for more than 60 weeks after the date of treatment commencement, the record of malignant tumor and adverse events leading to discontinuation that occur at and after Week 61 should include the following information.

Occurrence of a serious adverse reaction, an unexpected adverse reaction or other adverse reactions should be separately investigated in detail if determined necessary by Sponsor.

- Presence/absence of adverse event
- Name of adverse event
- Diagnosis of malignant tumor (only if malignant tumor occurs)
- Date of occurrence
- Intervention
- Seriousness
- Outcome at the completion of observation period
- Causal relationship

If the adverse event is associated with abnormal laboratory values, i.e., clinical laboratory tests, the following information should also be recorded.

- Laboratory parameter
- Site reference value
- Unit
- Date measured

• Results

Supplemental remarks: An adverse event is any unfavorable event (including a clinically significant abnormal laboratory change) occurring after administration of XELJANZ, whether or not related to XELJANZ. A serious adverse event is any event that results in death, is life-threatening, requires inpatient hospitalization or prolongation of existing hospitalization, results in persistent or significant disability/incapacity, is a congenital anomaly/birth defect, or any other medically important event that may lead to disability.

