6.1.1. Important identified risks

- Serious infection (including tuberculosis, pneumonia, Pneumocystis pneumonia, sepsis, and opportunistic infection)
- Herpes zoster
- Neutropenia, lymphopenia, oligochromemia
- Hepatic impairment
- Reactivation of hepatitis B virus
- Gastrointestinal perforation
- Interstitial lung disease
- Venous thrombosis

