6. ENDPOINTS AND COVARIATES

6.1. Safety Endpoints

The safety endpoints and their definition in this study are presented below. Events assessed as a safety endpoint will be those that developed from the start of treatment to the end of observation period or 60

weeks after the start of treatment, whichever came first, except for malignancies, for which all events occurring by the end of observation period will be assessed as a safety endpoint.

- Adverse reactions: Adverse events considered by the physician as treatment-related
- Adverse events (AEs): All-causality AEs
- Serious adverse events (SAEs) and serious adverse reactions: AEs and adverse reactions considered by the physician as serious
- Safety specification: The definition of the events considered as an element in the safety specification of this drug should follow the definition of the Important Identified Risks and Important Potential Risks presented in the Appendix of the latest Tofacitinib Periodic Safety Update Report (PSUR). Below is the definition at the time of the preparation of this SAP (3.0 version), except for hepatitis B virus reactivation, of which definition is given in this SAP below, because it is not defined in the PSUR.
 - Serious infections (including tuberculosis, pneumonia, pneumocystis pneumonia, sepsis, opportunistic infection): Events that are serious and coded as MedDRA SOC Infections and Infestations; MedDRA HLT Tuberculous infections, Mycobacteria identification and serology; MedDRA PT Febrile neutropenia, Asymptomatic COVID-19, Coronavirus infection, Coronavirus test positive, Coronavirus test, COVID-19 immunisation, COVID-19 pneumonia, COVID-19 prophylaxis, COVID-19 treatment, COVID-19, Exposure to SARS-CoV-2, Occupational exposure to SARS-CoV-2, SARS-CoV-2 antibody test, SARS-CoV-2 antibody test positive, SARS-CoV-2 carrier, SARS-CoV-2 sepsis, SARS-CoV-2 test false negative, SARS-CoV-2 test positive, SARS-CoV-2 test, SARS-CoV-2 viraemia, or Suspected COVID-19
 - Herpes zoster: Events coded as MedDRA PT Disseminated varicella zoster virus infection,
 Genital herpes zoster, Herpes zoster cutaneous disseminated, Herpes zoster
 disseminated, Herpes zoster infection neurological, Herpes zoster meningitis, Herpes zoster
 meningoencephalitis, Herpes zoster meningomyelitis, Herpes zoster necrotising retinopathy,
 Herpes zoster oticus, Herpes zoster pharyngitis, or Ophthalmic herpes zoster

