8.2.3.2. Adverse events

All adverse events

Adverse events will be summarized by SOC and PT in terms of number and proportion of patients.

• Serious and non-serious adverse events

SAEs will be summarized by SOC and PT in terms of number and proportion of patients. Similarly, non-serious AEs will be summarized by SOC and PT in terms of number and proportion of patients.

• Safety specification

The following AEs included in the scope of the safety specification will be summarized in terms of number and its proportion of patients, as well as incidence and its 95% CI.

- Serious infections (including tuberculosis, pneumonia, pneumocystis pneumonia, sepsis, and opportunistic infection)
- Herpes zoster
- Neutrophils decreased, lymphocytes decreased, haemoglobin decreased
- Hepatic function disorder

- Hepatitis B virus reactivation (in patients with past history or complication of hepatitis B virus carrier)
- Gastrointestinal perforation
- Interstitial lung diseases
- Venous thromboembolism
- Malignancy
- Cardiovascular events (including lipids increased and hyperlipidaemia)
- Cardiovascular events (excluding lipids increased and hyperlipidaemia)
- Lipids increased and hyperlipidaemia
- Rhabdomyolysis and myopathy

In addition, patients who experienced AEs in the scope of the safety specification will be summarized in terms of n and proportion by SOC and PT, for different kinds of action taken and outcome.

• Timing of onset of elements in the safety specification

Patients who experienced AEs of each element in the safety specification will be summarized by timing of first onset, in terms of n and proportion as well as incidence and its 95% CI. For the purpose of summarization by time to onset, the denominator to calculate the proportion will be the number of patients who took at least one dose during each time category, and the denominator to calculate the incidence will be the duration of exposure in each time category. The categories for onset timing will be given by [\leq 15 weeks, >15 to \leq 30 weeks, >30 to \leq 45 weeks, >45 to \leq 60 weeks], except for malignancy, for which given by [\leq 15 weeks, >15 to \leq 30 weeks, >30 to \leq 45 weeks, >45 to \leq 60 weeks, >60 to \leq 75 weeks, >75 to \leq 90 weeks, >90 to \leq 105 weeks, >105 to \leq 120 weeks, >120 to \leq 135 weeks].

• Relationship between concomitant drugs and adverse events

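### The protocol treats a medically important event as serious only if disability is possible, so some infections managed without admission may be missed in the Serious infections element

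*Protocol*

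**What the plan says.** The supplemental remarks in Protocol 7.3.11 define a serious adverse event. The limbs are death, an event that "is life-threatening, requires inpatient hospitalization or prolongation of existing hospitalization", lasting or marked disability, a congenital anomaly, and finally "or any other medically important event that may lead to disability". Neither document gives a wider definition of a medically important event. Seriousness is one of the items recorded for each adverse event under 7.3.11.

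The SAP sets no seriousness criteria of its own. Section 6.1 takes "AEs and adverse reactions considered by the physician as serious". It defines the Serious infections element as "Events that are serious and coded as MedDRA SOC Infections and Infestations", followed after semicolons by a tuberculosis high-level term group and a list of preferred terms. The matching risk in Protocol 6.1.1 is "Serious infection (including tuberculosis, pneumonia, Pneumocystis pneumonia, sepsis, and opportunistic infection".

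Other elements are built differently. For example, "Herpes zoster: Events coded as MedDRA PT Disseminated varicella zoster virus infection" opens a list of preferred terms with no seriousness condition.

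Events classed as non-serious are still reported. SAP 8.2.3.2 says: "Similarly, non-serious AEs will be summarized by SOC and PT in terms of number and proportion of patients".

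**The concern.** The last limb of a seriousness definition normally has to catch events that did not kill, hospitalise or disable but could have done so without treatment. Here it catches only potential disability. Actual disability has its own limb, so this one adds little, and it leaves out events that needed treatment to prevent death or admission.

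That matters because one headline safety element depends on the seriousness entry. Serious infection is the first important identified risk, and the diseases it names include some that can be managed without admission. If the protocol's wording steers a physician to record such a case as non-serious, the case leaves the element. In a post-approval safety surveillance, a missed event is the costly kind of error.

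**Working it through.** The plan has no figure that depends on the seriousness definition, so there is nothing to reproduce. The check sets the texts side by side, followed by an illustration on stated assumptions.

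**1. Which infections fall through.** Under Protocol 7.3.11 an infection is serious if any limb is met:

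- Fatal: serious.
- Life-threatening: serious, with or without admission.
- Admitted, or stay prolonged: serious.
- Disabling, or medically important and possibly disabling: serious.
- Managed without admission, not life-threatening, not potentially disabling, but treated to prevent death or admission: no limb is met.

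Only the last group is exposed.

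**2. How the entry reaches the analysis.** The physician's entry is taken as it stands (SAP 6.1). Serious infections is the only safety-specification element in SAP 6.1 that requires a serious entry. The others are defined by MedDRA terms or, for hepatitis B reactivation, by patient history and event type.

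**3. Which outputs are touched.**

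- Number, proportion, incidence and 95% CI of the element (SAP 8.2.3.1 and 8.2.3.2).
- Timing of first onset (same sections).
- Kaplan-Meier plots, and the risk ratio and risk difference between dose levels (SAP 8.2.3.3).

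The tables by system organ class and preferred term, including the non-serious table, and the listings (SAP 8.2.3 and 9) retain the cases. Those tables give no person-year incidence or Kaplan-Meier plot for the identified risk.

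**4. The semicolons in SAP 6.1.** If the word serious governs the whole definition, outpatient tuberculosis recorded as non-serious is lost. If it governs only the system organ class, tuberculosis coded to the high-level term counts whatever the entry. Pneumonia and Pneumocystis pneumonia counted through the system organ class remain gated on either reading. The text does not settle which is meant.

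**5. Size, on assumptions.** Let *f* be the fraction of patients with an infection that should count who are lost because it was recorded as non-serious. The count becomes (1 − *f*) times its value. With person-time held fixed, incidence falls in the same proportion. In practice the fall would be very slightly larger, because under SAP 8.1.4 a patient treated as event-free goes on accruing exposure, up to 60 weeks.

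Maximum person-time, from 470 patients (Protocol 7.5.1) each followed for the full 60 weeks: 470 × 60 / 52.18 = 540.4 person-years. Expected cases = rate × 540.4 / 100 × (1 − *f*). The rates and *f* are assumed; the documents give neither.

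| Assumed rate per 100 PY | *f* = 0 | *f* = 10% | *f* = 25% | *f* = 50% |
|---|---|---|---|---|
| 2 | 10.8 cases | 9.7 (rate 1.8) | 8.1 (1.5) | 5.4 (1.0) |
| 4 | 21.6 cases | 19.5 (3.6) | 16.2 (3.0) | 10.8 (2.0) |
| 6 | 32.4 cases | 29.2 (5.4) | 24.3 (4.5) | 16.2 (3.0) |

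Early discontinuation would lower the person-time and the counts, but not the relative loss.

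**6. Dose contrast.** With true risks *p*H and *p*L at the higher and lower dose levels and the same *f* in both, the observed ratio is (1 − *f*)*p*H / (1 − *f*)*p*L = *p*H / *p*L, which is unchanged. The observed difference is (1 − *f*)(*p*H − *p*L), which shrinks towards zero. The ratio moves only if *f* differs by dose.

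**The case against.** The strongest reply is that this is one narrowly worded clause with a limited reach. Several parts of that reply stand.

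- A reader might infer that dangerous infections treated without admission are non-serious as a class. The documents do not support this, because the life-threatening and potential-disability limbs need no admission.
- A reader might infer that the rates are certain to be biased downwards. They are not: the entry is the physician's judgement, and the case record form, a separate document in the protocol's reference list, may carry wider wording. Under-classification is a risk, not a known result.
- A reader might infer that no other element picks these infections up. Some are picked up without any seriousness condition: disseminated zoster under herpes zoster, neutropenic sepsis under the neutrophil element, certain abscesses under gastrointestinal perforation, and hepatitis B events in carriers under reactivation. That does not help ordinary pneumonia.
- The risk is named as serious infection, so its bracketed list can be read as kinds of serious infection, not as diseases that count regardless. The SAP also ties its definition to the periodic safety update report, so the gate may be a deliberate alignment. This is a good reason to keep the existing row. It does not make the seriousness standard behind that row any wider.

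The reply that the cases stay visible by preferred term is true but incomplete, since those tables do not give the incidence or timing reported for the identified risk.

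**Conclusion.** The point holds in a limited form. Protocol 7.3.11 ties medically important events to possible disability, neither document widens this, and SAP 6.1 makes a serious entry a condition of the Serious infections element. Infections that meet no other limb may therefore be missed in that element's number, proportion, incidence, onset timing, Kaplan-Meier plot and dose risk difference. Outpatient-managed pneumonia is the clear example. Tuberculosis is one only if the word serious governs the terms after the semicolons.

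The size cannot be derived. The relative loss of cases is at most the share of such infections recorded as non-serious, and it equals the outpatient share only if every outpatient case fails every limb and is marked non-serious. The tabulated figures rest on assumed rates and fractions. The documents do not support a claim that the loss is greatest for any particular infection. Nor do they support a claim that the dose risk ratio is distorted, which would need misclassification to differ by dose. Herpes zoster is unaffected.

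The conclusion assumes that physicians applied the protocol wording and that no wider definition was given to them elsewhere.

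**What to change.** 1. **Protocol 7.3.11.** Keep the opening of the last limb and replace its ending with: *that may endanger the patient or require treatment to prevent one of the outcomes above*. If the case record form or its guidance already used wider wording, say so.
2. **SAP 6.1, definition.** State whether the word serious governs the tuberculosis high-level term and the listed preferred terms, or only the system organ class.
3. **SAP 6.1, supplementary row.** Beside the row that follows the periodic safety update report, add one row counting tuberculosis, pneumonia, Pneumocystis pneumonia, sepsis and opportunistic infections regardless of the seriousness entry. Fix the MedDRA term list in advance, particularly for opportunistic infections, for which the SAP has none.

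The cost is a wording change, a term list and one extra row. No new data are needed, because all adverse events up to week 60 are collected whatever their seriousness (SAP 2.1). Under the wider limb a few more events would be classed as serious. Data collection was planned to end in June 2021 and SAP version 4.0 is dated 30 May 2022, so the rewording cannot change entries already made. For the final analysis, the supplementary row does the correcting.
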